7.3 Final Analysis

Draft TFLs will be provided after database lock. After Sponsor comments have been incorporated, the TFLs will be finalized and incorporated in the first draft CSR.

8.0 Data Review

8.1 Data Management

Data handling and transfer will take place under the PRA Data Management Plan for the study. All subjects who are screened will be entered in the database.

8.2 Acceptance of Data for Summarization

Programming of analysis datasets and TFLs may be ongoing during the data management of the study. However, programming of analysis datasets and TFLs will be completed and quality controlled (QC'd) after database lock. Only quality assured (QA'd) results released by the Safety Laboratory, Bioanalytical Laboratory, or other external data source will be used for the programming of analysis datasets and TFLs for the final report. Any data values requiring investigation or corrections that are identified while programming the analysis datasets and TFLs will be sent to the project Data Manager. If the issue affects the TFLs the Programmer or Statistician who identified the issue will follow it to resolution.

9.0 Definitions and General Analysis Methods

9.1 Analysis Data Presentation

9.1.1 Rounding

In listings data will be presented with the same precision as the original data. Derived data will be rounded for presentation purposes.

9.1.1.1 General

For summaries, the mean and median will be presented to one decimal place greater than the data, standard deviation to 2 greater than the data, and the minimum and maximum will be presented to the same number of decimal places as the data. Percentages will be presented with one decimal.

The above rule can be applied directly to collected data. For derived data rounding will occur prior to summarization (in the derived dataset as determined by the statistician) so a specific number of decimal places will have to be assumed to apply the above rounding rules for summary statistics.

9.1.1.2 Pharmacokinetic

Concentration data will be presented in listings as received by the vendor. Summary statistics of concentration data will be presented to 3 significant digits with the exception of %CV which will be presented to 1 decimal place.

PK parameter data will be rounded in the listings to an appropriate number of decimal places for presentation purposes only. Unrounded values (left as received in analysis dataset) will be used for all calculations of summary statistics and analyses for the summary tables. The summary statistics will be presented to the precision listed in the table in section 16.2.2. When significant digits are used for precision, all summary statistics will be presented to the same precision. When decimal places are used for precision, the rule outlined above in the General rounding section applies for summary statistics.

9.1.2 Imputation

Unless otherwise noted, data will not be imputed.

9.1.3 Daylight Savings Time Adjustments

On March 14, 2021 at 2:00 am the clocks change to 3:00 am for Daylight Savings Time. All clinic procedures for the remainder of the treatment period will be moved forward by one hour after daylight savings time occurs. All duration calculations (ie, AE duration, relative time from dosing for PK) for times post-daylight

savings time that will be relative to a time prior to daylight savings will need to be programmatically adjusted for the hour that was lost on the morning of March 14.

9.1.4 Descriptive Statistics

Unless otherwise indicated, continuous variables will be summarized with the following descriptive statistics and nomenclature: n = number of observations or subjects, mean = arithmetic mean, SD = standard deviation, Min = minimum value, median = median value, and Max = maximum value.

Categorical data will be summarized and presented with the following nomenclature: n = frequency and % = percentage. Percentages by categories will be based on the number of subjects exposed within a treatment.

For categorical data, the categories will be presented in the tables exactly as they appear in the case report form (CRF) / Database.

9.1.5 Pooling

No data pooling will be performed.

9.1.6 Unscheduled Measurements

Unscheduled and early termination measurements will be included in the listings. With the exception of unscheduled measurements used for baseline, unscheduled and early termination measurements will be excluded from the descriptive statistics and statistical analysis.

9.2 Analysis Data Definitions

9.2.1 Baseline Definition

Unless otherwise stated, baseline is defined as the last observation recorded before the study drug administration. The last observation can be an unscheduled / repeated measurement.

9.2.2 Treatment/Subject Grouping

Subjects will be assigned to one of the 4 renal function groups based on eGFR values at screening.

Label	Grouping
IMP	Apraglutide (TA799): a single 5 mg dose of apraglutide administered by SC injection to the abdomen.
Renal Function Group	Cohort 1: Severe Renal Impairment Cohort 2: Normal Healthy Match Cohort 3: Moderate Renal Impairment Cohort 4: Mild Renal Impairment

9.2.3 Common Variable Derivations

Variable	Data Type	Definition/Calculation
Change from baseline / predose	All	Postdose Observation minus baseline / predose Observation
Analysis Study Day (Prior to Dose)	All	Date of Measurement minus Dose Date
Analysis Study Day (Post Dose)	All	Date of Measurement minus Dose Date +1

TEAE	AE	AE is a TEAE if the AE Date/Time is greater than or equal to the Dose Date/Time
------	----	---

9.2.4 QC

The analysis datasets and the TFLs will be QC'd according to the general PRA EDS QC plan.

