7.1 Screening Visit

Screening Visit 1

Subjects will be screened within 28 days prior to administration of the IMP to confirm that they meet the subject selection criteria for the trial. The Investigator (or designee) will obtain informed consent from each subject in accordance ICH/GCP guidelines. If the time between screening and dosing exceeds 28 days as a result of unexpected delays (e.g., delayed drug shipment), then subjects do not require rescreening if the Day -1 laboratory results meet eligibility criteria. Maximum delay accepted between screening and IMP administration is a total of 42 days.

Subjects who qualified for this protocol but did not enroll from an earlier cohort/group may be used in a subsequent cohort/group without rescreening, provided the Day -1 laboratory results meet the eligibility criteria for this trial within 1 month after the date of screening.

The following procedures will be completed ([Table 1](#)):

- Obtain written informed consent
- Confirm and document that the subject meets the inclusion/exclusion criteria
- The Investigator or his/her designee will discuss with the subject the need to use highly effective contraception consistently and correctly according to the contraception guidelines and will confirm highly-effective, proper contraception is being used
- Collect demography (subject race, ethnicity, date of birth, age, sex)
- Collect height and weight and calculate BMI
- Obtain medical history, including history of prior illegal drug, alcohol and tobacco use
- Obtain complete medication history for all prescription or non-prescription drugs, and dietary and herbal supplements taken within 28 days prior to the planned dose
- Obtain a supine BP and heart rate after at least 5 minutes of rest in a supine position. One repeat measurement may be allowed at the discretion of the investigator
- Obtain body temperature
- Conduct a full physical examination (PE); this must be performed by trained medical personnel at the CRU
- Collect 12-lead ECG in triplicate after supine rest of 10 minutes or per CRU standard operating procedure
- Assess baseline symptoms/AEs
- If applicable, obtain as source document, prior/historical eGFR from the past 3 months using CKD-EPI equation (for Cohorts 1 [severe], 3 [moderate] and 4 [mild] only)
- Collect blood and urine specimens for the following:
 - Safety laboratory tests (hematology, clinical chemistry and urinalysis)
 - Urine drug or alcohol test

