10.1 Safety Data Reporting and Collection Period

After signing informed consent, all AEs including SAEs and AESIs regardless of relationship to apraglutide will be collected, fully investigated and documented in source documents and eCRFs and will be reported either until the last protocol-specific procedure or safety follow-up.

Investigators should report any SAEs, or other AEs of concern that are believed to be related to apraglutide for up to 2 weeks following the safety follow-up visit (EOT).

Adverse events that occur between subject's ICF signature and dosing will be captured as pre-treatment AEs.

The Investigator must monitor the condition of the subject throughout the trial from the time of obtaining informed consent until the last protocol-specific procedure, whether it is the EOT visit or ET visit, or a safety follow-up period.

If an Investigator becomes aware of an SAE which occurred up to 2 weeks following the safety follow-up visit (EOT) (this includes withdrawn subjects) and he/she assesses the SAE to have a reasonable possible causality to the IMP, the case will have to be reported to the Sponsor via the Contract Research Organization (CRO) (Section [10.3.3](#)).

The emergency contact details for the Sponsor can be found in the Investigator Site File (ISF).

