10.6 Severity Assessment

The Investigator will use the adjectives MILD, MODERATE, or SEVERE to describe the maximum intensity of the AE. For purposes of consistency, these are defined as follows:

- MILD: Does not interfere with subject's usual function
- MODERATE: Interferes to some extent with subject's usual function
- SEVERE: Interferes significantly with subject's usual function

Note the distinction between the severity and the seriousness of an AE. A severe event is not necessarily an SAE.

The NCI-CTCAE system [17] will be used to grade the severity of the SAEs, AEs and AESIs.

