17.1.1 Adverse Events

Treatment emergence will be evaluated for all AEs. Treatment-emergent adverse events (TEAE) are those that occur after the dose of study drug.

The following missing data will be imputed as defined (for calculations/summary tables only and will not be presented in listings):

- Missing AE start and / or end times for the calculation of onset and duration will be assumed to be at 00:01 for a start time and 23:59 for end times
- Missing AE severity or relationship will be assumed to be severe or related, respectively
- Missing AE start times for the determination of treatment emergence will be assumed to occur after treatment unless partial date documents the AE as happening prior to treatment
- Missing AE start date will be assumed to be after treatment for the determination of TEAE

A summary of number and percentage of subjects reporting TEAEs, TEAEs by severity and relationship, serious AEs (SAEs), and subjects who discontinued study drug due to an AE will be provided.

A summary of the number and percentage of subjects reporting each TEAE, and summary of total number of events, categorized by system organ class and preferred term coded according to the MedDRA, will be presented by renal function group and overall. Subjects will only be counted once within each body system or preferred term.

A summary of the number and percentage of subjects reporting each TEAE, and summary of total number of events, will be presented by relationship to study drug (as recorded on the eCRF) and by renal function group and overall. Subjects with multiple events within a system organ class or preferred term will be counted under the category of their most drug-related event within that system organ class or preferred term.

A summary of the number and percentage of subjects reporting each TEAE, and summary of total number of events, will be presented by severity (as recorded on eCRF) and by renal function group and overall.

Subjects with multiple events within a system organ class or preferred term will be counted under the category of their most severe event within that system organ class or preferred term.

A summary of the number and percentage of subjects reporting each SAE, and summary of total number of events, categorized by system organ class and preferred term coded according to the MedDRA, will be presented by renal function group and overall. Subjects will only be counted once within each body system or preferred term.

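### The SAP decides treatment emergence by AE start time alone, so a pre-dose AE that worsens after apraglutide is left out of the TEAE tables unless the eCRF instructions require a new record

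*SAP*

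**What the plan says.** The derivation table in SAP section 9.2.3 gives the programming rule: "AE is a TEAE if the AE Date/Time is greater than or equal to the Dose Date/Time". SAP section 17.1.1 gives the definition in words: "Treatment-emergent adverse events (TEAE) are those that occur after the dose of study drug". The imputation rules in that section show that the start of the event is what counts: "Missing AE start date will be assumed to be after treatment for the determination of TEAE".

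The protocol controls what enters the database. AEs are collected from consent onwards, and under section 10.1 those arising between "ICF signature and dosing will be captured as pre-treatment AEs". Section 10.6 fixes how intensity is recorded: "The Investigator will use the adjectives MILD, MODERATE, or SEVERE to describe the maximum intensity of the AE".

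Screening normally takes place within 28 days before dosing. Section 7.1 allows more for unexpected delays: "Maximum delay accepted between screening and IMP administration is a total of 42 days".

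Under SAP section 17.1.1 the tables by term, by relationship and by severity are confined to TEAEs. All recorded AEs, emergent or not, go into a by-subject listing. The SAE and AESI summaries are not worded as TEAE-only.

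**The concern.** A treatment-emergence rule should separate what was present before the drug from what appeared, or became worse, under it. This one captures only what appeared. Intensity is stored as a single maximum, so a complaint that was mild before the dose and severe after it becomes one record with a pre-dose start and a post-dose peak. The start keeps it out of the TEAE tables, and its severe grade sits on an event labelled pre-treatment.

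Such records are to be expected. The protocol has the site ask about baseline symptoms and AEs at screening, on Day -1 and again before dosing on Day 1, and section 10.8 has AEs followed until recovery. An AE open at the time of injection is therefore an ordinary case.

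The type, frequency and intensity of AEs form part of the secondary endpoint. In cohorts of about eight, one event left out is visible in a table.

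**Working it through.** The plan gives no figure to reproduce on this point. The check follows one event through the rules, then sizes its effect on a table.

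**Inputs**
- Emergence test: start at or after dose (SAP 9.2.3), after dose (SAP 17.1.1).
- Intensity: one maximum per AE (protocol 10.6).
- Label for AEs starting between consent and dosing: pre-treatment (protocol 10.1).
- Cohort size: 8; Part 1 total: 16 (protocol 3.1.1, SAP 6.0).
- Percentages are based on the subjects exposed (SAP 9.1.4).

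**Step 1: one event traced.** As an illustration, take nausea that starts as mild during screening, is still present at dosing and becomes severe on Day 2.

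| Recording practice | Record(s) | Start at or after dose? | In TEAE tables? |
|---|---|---|---|
| One record | start in screening, maximum severe | No | No |
| New record on worsening | (a) start in screening, mild | No | No |
| | (b) start Day 2, severe | Yes | Yes, as severe |

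The result depends entirely on how the site records the worsening. No section of either document tells the site which practice to follow.

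**Step 2: where the single record goes.**
- By-subject AE listing (16.2.7.1): included.
- Tables 14.3.1.2 (term), 14.3.1.3 (relationship) and 14.3.1.4 (severity): not included.
- TEAE rows of Table 14.3.1.1: not included.
- Tables 14.3.1.5 (SAE) and 14.3.1.6 (AESI): could be included if the event qualifies, since neither is worded as TEAE-only.

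**Step 3: comparison with the missing-data rules.** SAP 17.1.1 counts an AE with a missing start date as treatment-emergent, and assumes severe where severity is missing and related where relationship is missing. An event of unknown onset is therefore counted, while one documented as worsening after the dose is not. The rule is out of line with the caution the SAP shows elsewhere.

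**Step 4: size per affected subject.**
- One cohort: 1/8 = 12.5 percentage points.
- Part 1 overall: 1/16 = 6.25 percentage points.

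These are upper limits for a single subject. A term row shifts only if the subject has no other TEAE under that term. In the severity table a subject is counted once at the worst grade, so the omission can leave the subject in too low a row or out of the table. The any-TEAE percentage shifts only if the subject has no other TEAE at all.

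**Step 5: frequency.** The number of subjects with an AE open at dosing, and the share of those that worsen, are given nowhere in the documents. No expected count is calculated.

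The two SAP sections also differ for an AE timed exactly at the dose: 9.2.3 includes it and 17.1.1, read literally, does not.

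**The case against.** The strongest objection is that the loss depends on a document that has not been seen. SAP section 3.0 says the plan is to be read with the final eCRF dated 21-Sep-2020. If its completion instructions open a new record when an AE worsens, the start-time rule works, and protocol 10.6 does not forbid that. This stands, and the conclusion is conditional for that reason. It does not correct the SAP, whose definition would still rest on an unstated recording convention.

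A reader might infer that a worsening event disappears from everything except the listing. The documents do not support that. Oedema and abdominal pain may fall under the AESI categories of fluid overload and persistent abdominal pain (protocol 10.2), and would then be eligible for Table 14.3.1.6. A serious event would be eligible for Table 14.3.1.5.

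A reader might also infer that the undercount falls mainly on the severe renal impairment cohort and narrows the safety comparison with healthy controls. That is not supported either. Comorbidities present at the initial visit are medical history, and by implication of protocol 10.2 they become AEs if they worsen. If the site dates such an AE at the worsening it counts as a TEAE, although the dating rule is unwritten. Impaired subjects with comorbidities must be medically stable on a stable regimen, and chronic abdominal pain is an exclusion for everyone. What remains is new complaints that begin between consent and dosing, and nothing in the documents says these differ between cohorts.

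Finally, the practical stakes are limited. The endpoint is adverse events rather than TEAEs, safety is descriptive, about 16 subjects can be read one by one in the listing, and the move to Part 2 depends only on the AUC ratio. All of this stands, and it limits the weight of the point.

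**Conclusion.** The point holds in conditional form. As written, the SAP rule leaves an AE that starts between consent and dosing and worsens after apraglutide out of Tables 14.3.1.2 to 14.3.1.4 and the TEAE rows of 14.3.1.1, unless the eCRF instructions require a new record. The window is normally up to 28 days, and 42 at most. Nausea is the clean example because it is not in the AESI list.

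The effect is at most 12.5 percentage points per affected subject in a cohort row. For the any-TEAE rate, it applies only to a subject with no other TEAE. Neither the number of such subjects nor any difference between cohorts can be derived from the documents.

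This is an error in a stated rule, worth correcting before database lock. It does not touch the PK analysis or the decision to open Part 2.

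**What to change.** Two sentences are needed.

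1. In SAP sections 9.2.3 and 17.1.1, use one definition: a TEAE is an AE that starts at or after the dose, or that starts before the dose and worsens in severity at or after it. State which severity scale decides, since protocol 10.6 names both the three adjectives and NCI-CTCAE grades. The common wording also removes the difference between the two sections for an AE timed at the dose.
2. In the eCRF completion guideline, require a post-dose worsening of a pre-treatment AE to be entered as a new AE record with its own start date, time and severity. The pre-treatment record is closed at its pre-dose intensity.

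The SAP sentence alone cannot be programmed, because a single maximum intensity does not show when the maximum occurred. The guideline sentence alone would leave the SAP relying on a convention it does not state. If the guideline already contains this rule, only the SAP sentence is needed.

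The cost is one extra record per worsening and possibly slightly higher TEAE counts. Sample size, visit schedule and PK analysis are unaffected.

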9.2.4.1 Critical Data

The QC plan requires datasets be classified as critical or non-critical. As the primary objective of this study is to characterize the pharmacokinetics, the datasets considered critical are subject level = ADSL, and pharmacokinetic = ADPC and ADPP.

9.2.5 ADaM Datasets and Metadata

The analysis datasets will be generated in accordance with Clinical Data Interchange Standard Consortium (CDISC) Analysis Data Model (ADaM) Version 2.1.

ADaM compliant datasets will be delivered to the sponsor. A define.xml file version 2 with the corresponding metadata will be included. Analysis results metadata are excluded.

9.3 Software

The statistical analysis and reporting will be done using SAS® for Windows™ Version 9.4 or higher (SAS Institute, Inc.).

PK parameter calculations will primarily be done using Phoenix® WinNonlin® (WNL) version 8.1 or higher (Certara, L.P.). Additional PK computations may be performed in SAS®.

9.4 Statistical Methods

9.4.1 Statistical Outlier Determination

No statistical outlier analysis is planned.

9.4.2 Predetermined Covariates and Prognostic Factors

There are no predetermined covariates or prognostic factors.

9.4.3 Hypothesis Testing

No formal hypothesis testing will be done.

9.5 TFL Layout

Report layout will be according to the PRA EDS – ICH E3 compliant – CSR Template. The layout of TFLs will be according to the PRA EDS standards.

Table shells are provided with and approved as part of this SAP. Small changes to shell layout due to the nature of the data may be required after lock at the discretion of the PRA project statistician. Other changes to the shells may be out of scope. The TFLs will be provided as a single document in Adobe PDF format (in Letter format), and as individual files for each table, figure and listing in Rich Text Format (.rtf).

10.0 Analysis Sets

The following subject level Analysis Sets (populations) will be used for summaries in the study.

10.1 Safety Set

The Safety Set will consist of subjects who receive at least one dose of the investigational medicinal product (IMP). This set will be used for the safety data summaries and baseline characteristic summaries. This set will be analyzed as treated.

10.2 Pharmacokinetic Concentration Set

The PK concentration set is defined as all subjects assigned to the IMP and treated who have at least one quantifiable concentration measured. This set will be used for PK concentration summaries. This set will be analyzed as treated.

10.3 Pharmacokinetic Parameter Set

The PK parameter analysis set is defined as all subjects assigned to IMP and treated who have at least one of the PK parameters of primary interest measured. This set will be used for PK parameter summaries and primary analysis. This set will be analyzed as treated.

